8.6 DEMOGRAPHIC AND OTHER BASELINE CHARACTERISTICS

Demographic and baseline data will be summarized with descriptive statistics: mean standard deviation, minimum, median, and maximum values for continuous variables, and percentages for

categorical variables, by treatment arm, for the ITT population. Prior and concomitant medications will also be summarized with percentages in this fashion.

8.7 MEDICAL HISTORY

The percentage of subjects with abnormal medical history findings will be summarized by body system, by treatment arm, for the ITT population.

8.8 PRIOR AND CONCOMITANT MEDICATIONS

Prior medications are those that were used before the start of the trial (prior to Day 0). Concomitant medications are those used during the course of the trial (on or after Day 0). Partial stop dates of prior and concomitant medications will be assumed to be the latest possible date consistent with the partial date; start dates will not be imputed. Data for all prior and concomitant medications will be summarized with percentages by treatment arm, for the mITT population.

8.9 EFFICACY ANALYSES

The true treatment effect on the primary endpoint is $\delta = p_V - p_P$, where p_V and p_P denote the true population probabilities of the primary endpoint for VGX-3100 and Placebo, respectively. The primary hypothesis of superiority is:

$$H_0$$
: $\delta \leq 0$ vs. H_1 : $\delta > 0$.

A p-value for this hypothesis test and corresponding 95% confidence interval will be computed based on the method of Miettinen and Nurminen [29]. Superiority will be concluded if the one-sided p-value is <0.025 and the corresponding lower bound of the 95% CI exceeds zero.

The secondary efficacy endpoints will be analyzed in the same manner as the primary hypothesis, but without the hypothesis test p-values.

The histopathologic efficacy time frame is defined by those who have undergone a biopsy or surgical excision at any time starting from 14 days prior to the protocol-specified target date of Week 36. It also includes subjects who undergo early excision or biopsy on or after Dose 1 but prior to this time frame or subjects who have no endpoint data for this time frame; these subjects are considered as failures for the efficacy endpoints. Table 7 through Table 11 provide details for the definition of the endpoint responses.

An exploratory analysis will examine the relationship between the primary efficacy endpoint and also the secondary efficacy endpoints of regression and clearance individually and the Immunoscore results. Relationships will be examined by using logistic regression models which model the efficacy outcomes versus the Immunoscore results and treatment group as regressor variables.

An exploratory analyses will examine the relationship between the primary efficacy endpoint and a) miRNA results, b) DNA methylation results, c) colposcopy results, d) cytology results, and e) HPV results. Relationships will be examined by using logistic regression models which model the primary endpoint outcome versus these results and treatment group as regressor variables.

Other exploratory analyses will examine durability of clearance of HPV-16 and/or HPV-18 infection from cervical tissue at Weeks 62 and 88. Descriptive statistics will be utilized; percentages of subjects who cleared will be presented by time point or anatomic location and treatment group.

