8.2 RANDOMIZATION AND BLINDING

Subjects will be randomized (2 VGX-3100:1 Placebo) in a stratified manner according to a) the degree of CIN observed in the biopsy specimens at screening (CIN2 vs. CIN3), b) BMI category

(≤25 vs. >25 kg/m²) on Day 0, and c) age category (<25 years vs. ≥25 years) on Day 0. There will be no pre-determined number of subjects required to be randomized within each stratum. To ensure that milder CIN2 disease is not over-represented in the study, the percentage of subjects enrolled with CIN2 will not exceed 50% of the total enrolled. A group of sequential allocation numbers will be designated for use by each participating country.

The study is double-blinded.

8.3 SAMPLE SIZE/POWER

A sample of 198 subjects will be randomized to receive either 6 mg VGX-3100 or placebo IM followed by EP in a 2:1 ratio. This sample size provides 90% power to declare VGX-3100 superior to placebo, assuming the true proportion of subjects who achieve the primary endpoints is 35% and 14% for VGX-3100 and placebo, respectively. These proportions also incorporate missing data (~10%) classified as non-regressors (failures). The assumptions are based on the Phase 2 study results.

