8.16 SUBGROUP ANALYSES

Primary and secondary efficacy endpoints will be analyzed by history of exposure to prophylactic HPV vaccines.

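### Section 8.9 does not carry the randomization strata into the primary Miettinen-Nurminen test and interval; if the strata are prognostic, the analysis is mildly conservative.

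*Protocol*

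**What the plan says.** In protocol version 5.0, section 8.2 sets the allocation: "Subjects will be randomized (2 VGX-3100:1 Placebo) in a stratified manner according to a) the degree of CIN" (CIN2 or CIN3), b) BMI at or below 25 versus above 25 kg/m², "and c) age category (<25 years vs. ≥25 years) on Day 0". That makes 2 × 2 × 2 = 8 strata. The same section caps CIN2 at half of enrollment: "To ensure that milder CIN2 disease is not over-represented in the study".

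Section 8.9 defines the effect as p_V − p_P, where the two terms "denote the true population probabilities of the primary endpoint for VGX-3100 and Placebo, respectively". It then states: "A p-value for this hypothesis test and corresponding 95% confidence interval will be computed based on the method of Miettinen and Nurminen". The decision rule is: "Superiority will be concluded if the one-sided p-value is <0.025 and the corresponding lower bound of the 95% CI exceeds zero". No stratum, weight or covariate is named. The secondary efficacy endpoints follow the same method without p-values.

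Section 8.3 plans 198 subjects in a 2:1 ratio for 90% power at 35% versus 14%, using overall rates only. About 10% missing data, counted as failures, is already inside those rates.

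**The concern.** Stratified allocation balances the arms within strata. If the strata predict response, this removes between-stratum variation from the treatment difference. An analysis that pools all subjects still counts that variation in its standard error. The interval is then somewhat wider than it need be, the test rejects a true null less often than 2.5%, and some of the precision that the stratification could have given is not used.

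The error runs in the safe direction, so at stake is efficiency rather than a false positive. There is also a matter of pre-specification. Section 8.17 releases group-level efficacy results to the sponsor once Week 36 data are complete. A choice between stratified and crude analysis made after that would be made with the result known.

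**Working it through.** **Inputs from the protocol.** n_V = 132, n_P = 66 (198 at 2:1, section 8.3); p_V = 0.35, p_P = 0.14 (8.3); one-sided 0.025 (8.9); eight strata (8.2).

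**Step 1: reproduce the planned power with the unstratified test.**

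- Pooled rate: (132 × 0.35 + 66 × 0.14)/198 = 55.44/198 = 0.28.
- SE under the null: √[0.28 × 0.72 × (1/132 + 1/66)] = 0.0677.
- SE under the alternative: √[0.35 × 0.65/132 + 0.14 × 0.86/66] = 0.0596.
- Power: Φ[(0.21 − 1.96 × 0.0677)/0.0596] = Φ(1.30) = 90.3%.

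Exact enumeration of the unstratified Miettinen-Nurminen score test, with variance p̄(1 − p̄)(1/132 + 1/66) × 198/197, gives 90.8%. The stated 90% therefore reproduces.

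**Step 2: why the unstratified standard error can be too large.** Within an arm, p(1 − p) = average of p_s(1 − p_s) over strata + variance of p_s over strata. Stratified allocation largely removes the last term from the sampling error of the difference. The unstratified variance keeps it. If the stratum rates p_s are equal, that term is zero and nothing changes.

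**Step 3: simulation.** The documents give no response rates by stratum, so the following are assumptions:

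- CIN2 50%, BMI above 25 50%, age below 25 20%, all independent.
- Central lists with permuted blocks of 3.
- 40,000 trials per setting.

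The stratified statistic is D = Σ w_s d_s / Σ w_s, with w_s = n_Vs n_Ps / n_s and d_s the difference in stratum s. Its variance is Σ w_s² v_s / (Σ w_s)², with v_s = p̄_s(1 − p̄_s)(1/n_Vs + 1/n_Ps) × n_s/(n_s − 1). In the table, U is unstratified and S is stratified.

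| Odds ratios (CIN, BMI, age) | Power U | Power S | Size at 14%, U / S | Size at 28%, U / S | Mean SE of U ÷ true SD |
|---|---|---|---|---|---|
| 1, 1, 1 | 90.6% | 90.6% | 2.2% / 2.2% | 2.4% / 2.4% | 0.99 |
| 1.5, 1.2, 1.2 | 90.7% | 90.7% | 2.2% / 2.2% | 2.3% / 2.3% | 1.00 |
| 2, 1.5, 1.5 | 91.0% | 91.4% | 2.2% / 2.3% | 2.2% / 2.3% | 1.01 |
| 3, 2, 2 | 91.3% | 92.6% | 2.0% / 2.4% | 1.9% / 2.4% | 1.03 |
| 5, 2, 2 | 91.7% | 93.6% | 1.8% / 2.2% | 1.7% / 2.3% | 1.05 |
| 5, 3, 3 | 92.0% | 94.5% | 1.6% / 2.2% | 1.4% / 2.4% | 1.07 |

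The largest power gap is 94.5 − 92.0 = 2.5 points.

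**Step 4: how much of the shortfall below 2.5% is discreteness.** Exact enumeration under simple randomization, with no strata at all, gives size 2.25% at a 14% rate and 2.42% at 28%. Part of the shortfall in the table would therefore be there anyway.

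**Step 5: sensitivity to the allocation lists.** Section 8.2 says allocation numbers are grouped by country, and the synopsis allows up to 25 countries. Suppose each country has its own stratum lists, with uneven country sizes (assumed; 10,000 trials per setting). With non-prognostic strata, power goes from 90.1% unstratified to 89.6% stratified with blocks of 3, or 89.3% with blocks of 6: a cost of 0.5 to 0.8 point. At odds ratios 4, 2, 2 the unstratified size is 2.0% to 2.1%, against 1.6% with central lists, and the stratified test still gains about 1.7 to 2.0 points of power.

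**Step 6: cell sizes.** Placebo subjects per stratum average 66/8 ≈ 8, with about 8 × 0.14 ≈ 1 responder. Sparse cells are therefore likely, and a pooling rule is needed.

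**The case against.** Section 8.9 never says that the test is unstratified. A stratified form of the Miettinen-Nurminen method exists, and the SAP, which is not at hand, may specify it. Defining the effect as p_V − p_P does not rule out a stratified estimator. This stands as a caution. Even so, the natural reading of 8.9 is unstratified: section 8.11.1 cites the method in the same bare way for adverse events, where no strata are in play, and the sample size reproduces from the two overall rates. If the SAP already stratifies, a clarifying phrase in 8.9 settles the point.

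A reader might infer that the interval is certainly too wide, that the test certainly runs below 2.5%, and that the trial loses planned power. The documents do not support this. They give no rates by stratum. The only hint of prognostic value is that CIN2 is treated as the milder disease; nothing of the kind is said for BMI or age. With no or weak prognostic effect the two tests are indistinguishable.

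A reader might also conclude that stratifying is free in every design, or that the effect will never be shown by CIN grade because section 8.16 names only one subgroup ("Primary and secondary efficacy endpoints will be analyzed by history of exposure to prophylactic HPV vaccines"). The first depends on block and list details that the protocol does not state (step 5). The second reads too much into silence: further subgroups are ordinary SAP content.

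**Conclusion.** The point holds in a conditional and modest form. The protocol stratifies the randomization on three factors, and its stated primary test uses none of them. If the factors are prognostic, the unstratified standard error is up to about 7% too large, one-sided size drops to about 1.6% at a 14% rate (1.4% at 28%), and power is up to about 2.5 points below a stratified test. Those upper figures need odds ratios of 5 for CIN grade and 3 each for BMI and age; at 2, 1.5 and 1.5 the power gap is 0.4 point.

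In every scenario the unstratified test keeps at least the planned 90% power, and type I error is never inflated. This is a worthwhile improvement, not a threat to validity. All sizes rest on the assumed odds ratios, stratum prevalences and block design.

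**What to change.** In section 8.9, before the Week 36 group-level release, state that:

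- the primary p-value and 95% confidence interval use the stratified Miettinen-Nurminen method with Mantel-Haenszel weights over the randomization strata;
- sparse cells are pooled by a rule fixed in advance that always keeps CIN2 and CIN3 separate;
- the unstratified analysis is reported as supportive.

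If the SAP already says this, a cross-reference is enough.

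The cost is wording, with no new data and no change to N = 198. If the strata are not prognostic, the stratified test gives up about 0.1 point of power with central lists, and possibly up to about 0.8 point if lists are also split by country. In that last case power would be 89.3%, just under the planned figure. The pooling rule has to be written now because 66 placebo subjects are spread over eight strata.

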3.4 EXPLORATORY OBJECTIVES AND ASSOCIATED ENDPOINTS

Exploratory Objectives	Associated Endpoints	
Evaluate tissue immune responses to VGX-3100 in cervical samples	1. Assessment of markers including but not limited to CD8+ and FoxP3+ infiltrating cells. Additional assessments may include visualization of Granulysin, Perforin, CD137, CD103 and PD-L1 in cervical tissue as sample allows. Markers listed here may change as new relevant information becomes available	
2. Describe association of microRNA (miRNA) profiles, DNA methylation profile, previous colposcopy, cytology and HPV testing results with Week 36 histologic regression	2. Colposcopy, cytology, and HPV test results (Weeks 8, 15 and 28 visits), miRNA profile (baseline, Week 8) and DNA methylation profile (baseline, Week 15) in conjunction with histologic regression of cervical HSIL at Week 36 visit	
3. Describe the durability of virologic clearance of HPV-16 and/or HPV-18 for subjects treated with VGX-3100 compared with those treated with placebo	3. Proportion of subjects with no evidence of HPV-16 and/or HPV-18 by type specific HPV testing at Weeks 62 and 88 visits	
4. Describe the patient-reported outcomes for subjects treated with VGX-3100	4. Patient-reported outcome questionnaires will be self-administered at baseline, Weeks 4, and 12, 8-14 days following each dose, and at Weeks 28, 36, 40 and 88 by subjects enrolled in US, Canada, Mexico, Germany and UK.	
5. Determine whether a tissue-based score derived using an immunologic markers (Immunoscore) at baseline is predictive for histological and virological response to VGX-3100 at Week 36	6 Immunoscore results for VGX-3100 treated subjects and in conjunction with histological and virological outcomes at Week 36	

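### The marker models in Section 8.9 do not match the exploratory objectives they serve, in marker effect, population or outcome

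*Protocol*

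**What the plan says.** All references are to protocol version 5.0.

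- **Immunoscore model (Section 8.9).** The primary endpoint, and regression and clearance separately, are analysed with "logistic regression models which model the efficacy outcomes versus the Immunoscore results and treatment group as regressor variables".
- **Immunoscore objective (Section 3.4, objective 5).** The question is whether the baseline score "is predictive for histological and virological response to VGX-3100 at Week 36". The endpoint is "Immunoscore results for VGX-3100 treated subjects and in conjunction with histological and virological outcomes at Week 36".
- **Same objective elsewhere.** The synopsis and Section 8.1 describe it as an association.
- **Other markers, model (Section 8.9).** "An exploratory analyses will examine the relationship between the primary efficacy endpoint and a) miRNA results, b) DNA methylation results", followed by colposcopy, cytology and HPV results. The models "model the primary endpoint outcome versus these results and treatment group as regressor variables".
- **Other markers, objective 2 (synopsis and Section 3.4).** The aim is to describe association with histologic regression at Week 36. The endpoint takes the marker results "in conjunction with histologic regression of cervical HSIL at Week 36 visit".
- **miRNA and DNA methylation (Section 6.9).** Day 0 samples are to be used to explore algorithms that predict response to VGX-3100. No such aim is stated for colposcopy, cytology or HPV results.

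**The concern.** Section 1.1.4 justifies the placebo arm by the fact that cervical HSIL can regress spontaneously. For any marker associated with outcome, the obvious competing explanation is therefore that it identifies women who would regress anyway. A model with one marker coefficient shared by both arms cannot address that explanation. It also does not match an endpoint defined in VGX-3100-treated subjects, because placebo subjects contribute to the same coefficient. A prognostic marker could then be read as one that predicts vaccine response.

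The second mismatch is in the outcome. The composite requires both absence of HSIL and absence of HPV-16/18 at Week 36 (Section 2.1.3). Objective 2 asks about the histologic part alone. As written, Section 8.9 contains no model of that outcome for miRNA, methylation, colposcopy, cytology or HPV results.

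**Working it through.** **The plan's own figure.** Section 8.3 gives 198 subjects, 2:1, 35% versus 14%, 90% power; Section 8.9 gives one-sided 0.025.
- Pooled rate: (2 × 0.35 + 0.14)/3 = 0.28.
- Null SE: √[0.28 × 0.72 × (1/132 + 1/66)] = 0.0677.
- Alternative SE: √[0.35 × 0.65/132 + 0.14 × 0.86/66] = 0.0596.
- Power: Φ[(0.21 − 1.96 × 0.0677)/0.0596] = Φ(1.30) = 0.903.
- Exact binomial power of the Miettinen-Nurminen score test is 0.908.

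The 90% reproduces. The protocol states no power for the marker models.

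**What the pooled coefficient estimates.** The information about a marker's log odds ratio in each arm is roughly proportional to n·p·(1 − p).
- VGX-3100: 132 × 0.35 × 0.65 = 30.0.
- Placebo: 66 × 0.14 × 0.86 = 7.9.
- VGX-3100 share: 30.0/37.9 = 79%.

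The pooled log odds ratio is therefore close to 0.79 × (VGX-3100 value) + 0.21 × (placebo value). A true odds ratio of 3 on VGX-3100 and 1 on placebo gives about exp(0.79 × ln 3) = 2.4; the large-sample fit gives 2.37. The pooled estimate is diluted, not empty.

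**Can it separate the two kinds of marker?** The documents give no marker distribution or effect, so a binary marker with 50% prevalence is assumed. Each row is 3,000 simulated trials of 132 and 66 subjects with marginal rates of 35% and 14%. Entries are the proportion with two-sided p < 0.05; interaction fits that did not converge count as not significant.

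| Marker OR, VGX-3100 / placebo | Large-sample common OR | Marker term, named model | Interaction | Marker term, VGX-3100 arm only |
|---|---|---|---|---|
| 3 / 3 | 3.00 | 91.2% | 3.0% | 83.9% |
| 3 / 1 | 2.37 | 73.1% | 26.4% | 83.1% |
| 4 / 1 | 2.95 | 90.6% | 37.2% | 96.4% |
| 5 / 1 | not computed | 96.0% | 49.6% | 98.5% |

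Rows 1 and 3 are opposite situations, one purely prognostic and one specific to VGX-3100. The named model gives nearly the same odds ratio and the same detection rate for both. The VGX-3100-only model matches the stated endpoint and has good power, but by itself it does not separate the two either (83.9% in row 1). The placebo estimate is needed for that.

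**Outcome, side by side.** For objective 2, the synopsis and Section 3.4 both name histologic regression in objective and endpoint. Section 8.9 names the primary endpoint. The Immunoscore paragraph of Section 8.9 lists regression and clearance as separate outcomes in addition to the composite; the paragraph for the other markers does not.

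**The case against.** The strongest counter-argument is that these are association analyses. The synopsis and Section 8.1 say so for the Immunoscore, objective 2 says so for the other markers, and a model with marker and treatment group can describe an association. This stands for colposcopy, cytology and HPV results, which carry only a descriptive aim. It does not dispose of Section 3.4 objective 5 or Section 6.9, where prediction of response to VGX-3100 is the stated aim.

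It can also be said that Section 8.9 names no interaction but does not rule one out, and that the SAP, which is not shown, may add terms. That is fair. The point rests on what the protocol itself fixes: the regressors, a two-arm population and the outcome, which do not agree with its own objectives.

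Three stronger readings are tempting, and the documents do not support them.
- *The additive model produces false positives.* Simulating a continuous, purely prognostic marker (log odds ratio 0.7 per SD) gives about 98% detection. That marker truly is associated with outcome, so this is power for association. It becomes an error only if the result is reported as specific to VGX-3100, and Section 8.9 sets no such labelling or patient-selection rule.
- *The composite is the wrong outcome.* It is the trial's primary endpoint, chosen because HPV persistence matters clinically (Section 2.1). The documents conflict; they do not show which outcome was intended.
- *The association with HPV results is mechanical.* The listed results come from Weeks 8, 15 and 28, not Week 36. Correlation with Week 36 clearance is to be expected from persistent infection, but the same measurement is not used twice.

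**Conclusion.** The point holds as a mismatch between Section 8.9 and the objectives it serves. First, for Immunoscore, miRNA and DNA methylation, the named model gives one pooled marker effect and cannot distinguish a prognostic marker from one of response to VGX-3100. That follows from the form of the model; the sizes (common odds ratios of 3.0 and 2.95, each detected in about 91% of trials) rest on the assumed binary marker at 50% prevalence and on Section 8.3's response rates. For the Immunoscore the model also covers a wider population than its endpoint, and the protocol alternates between prediction and association. Second, the outcome named for objective 2 is not modelled as written.

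The consequence is limited to what the exploratory analyses can conclude. A reader might infer that an interaction test settles the matter; it does not, since its power is only about 26% to 50% in the scenarios above.

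**What to change.** 1. For Immunoscore, miRNA and DNA methylation, report the marker odds ratio with 95% CI within each arm. The VGX-3100 estimate matches the stated Immunoscore endpoint; placebo is the control for spontaneous regression.
2. Give the treatment-by-marker interaction as an estimate with its CI, not as a decisive test.
3. Use one description, predictive or association, in the synopsis and Sections 3.4, 8.1 and 8.9, and state the population.
4. For objective 2, model Week 36 histologic regression and keep the composite as an additional outcome. Note that earlier HPV results are expected to correlate with its clearance component.

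The cost is a text change and a few more model fits. No new data are needed, and histologic regression is already a secondary endpoint. The drawback is imprecision: at 14%, the placebo arm would have about 66 × 0.14 = 9 composite responders, so its odds ratios and the interaction will have wide intervals and should be presented that way.

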8.10 IMMUNOGENICITY ANALYSES

Post-baseline cellular and humoral responses will be compared between treatment groups using a difference in medians and associated exact non-parametric 95% CI. Increases from baseline in interferon-γ ELISpot response magnitudes and HPV E6 and E7 titers from ELISA at Weeks 15 and 36 visits will be evaluated. Increases from baseline in CD8+/CD137+ PBMCs Perforin+ results at the Week 15 visit will be evaluated.

Changes from baseline in tissue response will be compared between treatment groups using a difference in means and associated t-distribution based 95% CIs.

Valid samples for statistical analysis purposes will be those collected within 7 or 14 days of the specified time points (see Table 1). Baseline is defined as the last measurement prior to the first treatment administration.

The mITT population will be used for immunogenicity analyses.

8.11 SAFETY ANALYSES

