8.10 IMMUNOGENICITY ANALYSES

Post-baseline cellular and humoral responses will be compared between treatment groups using a difference in medians and associated exact non-parametric 95% CI. Increases from baseline in interferon-γ ELISpot response magnitudes and in CD8+ / CD137+ PBMCs Perforin+ results and HPV E6 and E7 titers from ELISA at Weeks 8, 15 and 36 visits will be evaluated.

Post-baseline tissue response magnitude will be compared between treatment groups using a difference in means and associated t-distribution based 95% CIs.

Valid samples for statistical analysis purposes will be those collected within 7 or 14 days of the specified time points (see Table 1). Baseline is defined as the last measurement prior to the first treatment administration.

The mITT population will be used for immunogenicity analyses.

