^a No evidence of HSIL is defined by histology as negative, squamous atypia, or LSIL

Table 11: Definition of Secondary Clearance Endpoint Responder and Non-Responder

Responder	Non-Responder
Subject with no histologic evidence of HPV-16 and/or HPV-18 at Week 36 visit ^a AND Subject in which an excision or biopsy sample ^b was NOT obtained between initial dose up to Week 36 visit	Subject with evidence of HPV-16 or HPV-18 at Week 36 visit OR Subject in which an excision or biopsy sample ^b was obtained between initial dose up to Week 36 visit OR Subjects with no Week 36 visit sample result

^a The efficacy time frame is defined by those who have undergone HPV testing at any time starting from 14 days prior to the protocol-specified target date of Week 36. The first tissue removal sample within the time frame determines the histology endpoint. The most recent HPV clearance result prior to tissue removal, which includes results from the same date, within the time frame determines the HPV clearance endpoint.

^b The efficacy time frame is defined by those who have undergone a biopsy or surgical excision at any time starting from 14 days prior to the protocol-specified target date of Week 36. The first tissue removal sample within the time frame determines the histology endpoint. The most recent HPV clearance result prior to tissue removal, which includes results from the same date, within the time frame determines the HPV clearance endpoint.

^c Excludes ECC-only samples

^b Excludes ECC-only samples

2.1.4 IMMUNOGENICITY ASSESSMENT

Humoral and cell mediated immune responses in response to VGX-3100 treatment will be evaluated in blood samples taken at baseline (both screening as well as Day 0 prior to dosing) and at Weeks 15 and 36. Cervical tissue samples will also be analyzed for evidence of elevated immune responses at Week 36 as compared to baseline (screening).

If there is residual tissue in the paraffin block after histologic diagnoses have been rendered, then unstained slides and/or the relevant paraffin blocks may be collected for immunohistochemistry (IHC). Whenever possible, these studies may be performed on tissue sections from the diagnostic screening biopsy (pre-dose) and from tissue obtained post-dose(s) (Week 36).

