6.10 TISSUE IMMUNOGENICITY ASSESSMENT

If there is residual tissue or additional slides in the paraffin block after histologic diagnoses have been rendered, then unstained slides and/or the relevant paraffin blocks may be collected for immune assessment. Available tissue collected from pre- and post- treatment may be assessed for the presence of immune cells using immunohistochemistry or immunofluorescence. The presence of immune signatures may also be analyzed through the assessment of various transcripts suggestive of an inflammatory or an immunosuppressive tissue microenvironment.

An Immunoscore algorithm will be applied to cervical tissue obtained at baseline. The algorithm is composed of scoring patients based on infiltration of immune cells stained with CD8, FoxP3, CD103 and Perforin. Scoring will occur in epithelium designated as HSIL.

For HSIL epithelium, 1 point will be assigned for patients who show at least two of the following three parameters:

- CD8 count per mm $^2 > 375$,
- perforin count per per $mm^2 > 0$ and
- CD103 count per per $mm^2 > 150$

Additionally, 1 point will be assigned for each for the following parameters:

- FoxP3/CD8 ratio <1:3,
- CD103/CD8 ratio >2:1,
- CD103/ perforin ratio >10:1 and
- CD103/FoxP3 ration > 1.5:1

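### Section 8.10 compares raw change from baseline in tissue immune response, which is valid but less precise than adjusting for the screening value already collected

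*Protocol*

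**What the plan says.** Section 8.10 of the current protocol (version 5.0) fixes the outcome variable, the estimator and the interval for the tissue analysis: "Changes from baseline in tissue response will be compared between treatment groups using a difference in means and associated t-distribution based 95% CIs". The same section states "Baseline is defined as the last measurement prior to the first treatment administration" and "The mITT population will be used for immunogenicity analyses". Section 2.1.4 names the two time points, the screening biopsy and the Week 36 tissue.

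Section 3.4 lists the objective as exploratory: "Evaluate tissue immune responses to VGX-3100 in cervical samples". Section 6.10 makes the material conditional on what is left over: "If there is residual tissue or additional slides in the paraffin block after histologic diagnoses have been rendered". No section adds the baseline value as a covariate to this comparison, and none gives an SD, a correlation, an effect size or a power for it.

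**The concern.** In women with both samples the screening value is already in hand. Subtracting it forces the baseline coefficient to be exactly 1. ANCOVA estimates that coefficient from the data. If the true slope of the Week 36 value on baseline is below 1, the subtraction adds baseline noise to the comparison.

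A slope well below 1 is plausible here, though this is inference. Baseline tissue is HSIL. Week 36 tissue may have regressed, and under Tables 4 and 5 it may come from a four-quadrant biopsy or an excision. What is at stake is the width of the confidence interval for a marker comparison whose sample is already reduced to women with residual tissue.

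**Working it through.** **Inputs.** Trial size and allocation come from Section 8.3: "A sample of 198 subjects will be randomized to receive either 6 mg VGX-3100 or placebo IM followed by EP in a 2:1 ratio", that is 132 and 66 women, an upper limit for the tissue analysis. The SDs s0 (baseline) and s1 (Week 36) and the correlation rho are assumptions, taken as common to both arms.

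**The plan's own figure.** The only stated power is 90% for the primary endpoint (35% versus 14%). It reproduces: 90.3% by the pooled normal formula and 90.8% by exact enumeration of the Miettinen-Nurminen test. It says nothing about the tissue comparison.

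**Per-subject variances.**

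- Raw change: s0^2 + s1^2 - 2*rho*s0*s1
- Week 36 value alone: s1^2
- ANCOVA (Week 36 value or change, adjusted for baseline): s1^2*(1 - rho^2)

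Raw change minus ANCOVA = s0^2 - 2*rho*s0*s1 + rho^2*s1^2 = (s0 - rho*s1)^2. This is never negative, and it is zero only if rho*s1/s0 = 1. Raw change is noisier than the Week 36 value alone when s0^2 < 2*rho*s0*s1 fails strictly, that is when rho < s0/(2*s1). With equal SDs that threshold is 0.5.

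**Numbers** (variances in units of s0^2; the CI width ratio is the square root of the variance ratio):

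| s1/s0 | rho | Raw change | ANCOVA | Variance ratio | Width ratio | Adjusted CI narrower by |
|---|---|---|---|---|---|---|
| 1 | 0.3 | 1.40 | 0.91 | 0.65 | 0.81 | 19% |
| 1 | 0.5 | 1.00 | 0.75 | 0.75 | 0.87 | 13% |
| 1 | 0.7 | 0.60 | 0.51 | 0.85 | 0.92 | 8% |
| 1.5 | 0.5 | 1.75 | 1.69 | 0.96 | 0.98 | 2% |
| 2/3 (0.67) | 0.5 | 0.78 | 0.33 | 0.43 | 0.65 | 35% |

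With equal SDs the variance ratio reduces to (1 + rho)/2.

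**Against the Week 36 value alone.** At rho = 0.5, raw change is better if s1 = 1.5*s0 (1.75 against 1.5^2 = 2.25), equal if s1 = s0, and worse if s1 = 2/3*s0 (0.78 against (2/3)^2 = 0.44).

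**Simulation.** With 66 and 132 subjects, equal SDs and 4000 runs, the variance of raw change divided by that of ANCOVA was 1.65, 1.33 and 1.15 at rho = 0.2, 0.5 and 0.7. The formula 2/(1 + rho) gives 1.67, 1.33 and 1.18.

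**The case against.** The strongest reply is that the planned method is valid. In a randomised comparison, a difference in mean change is unbiased and its t interval has its nominal coverage, apart from selection by tissue availability. It also answers directly the question of whether responses rose from screening. The endpoint is exploratory, its marker panel may change, and no decision depends on it. All of this stands, and it keeps the point small. It does not make the choice neutral, because adjustment addresses the same between-arm question with the same women.

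A second reply is that covariates for an exploratory marker belong in the SAP, which is not at hand. But Section 8.10 does not leave the matter open: it states the analysis, and an SAP using ANCOVA would depart from it.

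Third, the size of the gain is unknown. This also stands. The reasons for expecting a low correlation also make equal SDs doubtful, so 8% to 19% is not the full range.

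Several stronger readings are tempting and are not supported:

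- A reader might infer bias or an inflated error rate. The loss is of precision only.
- A reader might infer that raw change is worse than ignoring baseline, and so worse than the superseded version 4.0, which had "Post-baseline tissue response magnitude will be compared between treatment groups using a difference in means and associated t-distribution based 95% CIs". That needs rho < s0/(2*s1), and the protocol does not show on which side of this threshold the trial lies.
- A reader might turn the variance ratio into a gain in power. Section 8.10 plans an interval for this endpoint and no test, so such figures would describe an analysis that is not planned.

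**Conclusion.** The point holds as a minor improvement in efficiency. Section 8.10 fixes an analysis that gives away precision by (s0 - rho*s1)^2 per subject, although the value needed to recover it is already collected.

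In the cases worked here, the adjusted interval is between about 2% and 35% narrower. These figures rest on assumed rho and SDs, on the same SDs and correlation in both arms, and on a linear relation between the two values. That adjustment cannot lose is a large-sample statement: in a small sample it spends one degree of freedom and pays a little for chance imbalance in baseline. Adjustment does not repair selection by tissue availability. The primary result and the study's conduct are untouched.

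**What to change.** In Section 8.10, replace the tissue sentence with an ANCOVA: regress the Week 36 tissue value on treatment and baseline value, in women with both samples, on the planned measurement scale. Report the adjusted difference between arms with its 95% CI, and keep mean change by arm as a descriptive summary. Using change as the outcome in the same model gives the same treatment estimate, so the change wording can stay if the sponsor prefers it.

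No log transformation is needed for this. The Immunoscore rule in Section 6.10 gives credit for a perforin count above zero, so zeros are to be expected, and logging would also change the quantity being estimated.

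The cost is one sentence, a standard model and one degree of freedom. A change score already requires both samples, so no women are lost and no new data are needed.
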